3.6 Immunogenicity

ADA incidence rate and titer will be tabulated for each treatment group at baseline and postbaseline visits. Samples confirmed positive for ADA will be tested and analyzed for nAb titer and summarized similarly. For overall post-baseline summary, persistent positive is defined as positive at ≥ 2 post-baseline assessments (with ≥ 16 weeks between first and last positive) or positive at last post-baseline assessment; transient positive is defined as negative at last post-baseline assessment and positive at only one post-baseline assessment or at ≥ 2 postbaseline assessments (with <16 weeks between first and last positive).

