1.6.2 Secondary Hypotheses

1. Repeat dosing with MEDI6012 will result in a pharmacokinetic (PK) profile (lecithin-cholesterol acyltransferase [LCAT] mass and LCAT activity) that allows once weekly or more frequent dosing.

- 2. A regimen comprised of an initial loading dose of MEDI6012 followed by a dose at 48 hours and 1 week later will result in a rapid rise in HDL-C and apoA1 compared with no loading dose and maintenance of pharmacodynamic (PD) effect for 7 or more days.
- 3. Repeat dosing with MEDI6012 results in dose-dependent responses for other key pharmacodynamic (PD) biomarkers in subjects with stable atherosclerotic CVD.
- 4. Repeat dosing with MEDI6012 does not result in the development of neutralizing antidrug antibodies (nAb) that cross-react with endogenous LCAT leading to decreased HDL-C.

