4.8.4 Immunogenicity

ADA incidence rate and titer will be tabulated for each treatment group. Samples confirmed positive for ADA will be tested and analyzed for nAb and summarized similarly.

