2.1.2 Secondary Study Objectives

- 1. To establish the PK profile of MEDI6012 following repeat dose administration.
- 2. To establish the PD effect of MEDI6012 following an initial loading dose followed by a dose at 48 hours and 1 week later (Cohort 4 only).
- 3. To evaluate the effect of MEDI6012 on a range of PD biomarkers following repeat dose administration.

4. To evaluate the immunogenicity potential of MEDI6012.

Secondary Endpoints:

- 1. PK for MEDI6012 mass and activity
- Serum concentration of other key lipids and lipoproteins: CE, HDL-CE, HDLunesterified cholesterol (HDL-UC), non-HDL-C, non HDL CE, non-HDL-UC, low density lipoprotein cholesterol (LDL-C), total cholesterol (TC), apolipoprotein B (apoB), triglycerides (TG), very low-density lipoprotein-cholesterol (VLDL-C), and apolipoprotein A1 (apoA1), apoAII, apoCIII, apolipoprotein E (apoE), pre-beta1 high-density lipoprotein (preβ1-HDL).
- 3. Anti-drug antibodies (ADA) and nAb development, with concomitant decreases in HDL-C

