3.2 Analysis Populations

The analysis populations are defined in Table 3.2-1.

Population	Description
As-treated population	Subjects who receive any study investigational product will be included in the as-treated population and subjects will be analyzed according to the treatment they actually receive.
PK population	Subjects in the as-treated population who have at least one detectable LCAT serum concentration measurement
Immunogenicity population	Immunogenicity population includes all subjects in the as-treated population who have at least one serum sample for immunogenicity testing

Table 3.2-1Analysis Populations

The primary analysis of the safety and PD endpoints will be assessed based on As-treated population. The PK data will be analyzed in PK population. Immunogenicity data will be assessed using immunogenicity population.

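### The persistent and transient ADA classes in SAP 3.6 have no baseline condition, so a subject with stable pre-existing antibody is classed like one who seroconverted

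*SAP*

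**What the plan says.** SAP 2.1.2 words the secondary endpoint as "Anti-drug antibodies (ADA) and nAb development, with concomitant decreases in HDL-C". It serves the objective on the drug's immunogenicity potential. The fourth secondary hypothesis (Protocol 1.6.2) likewise concerns neutralizing antibodies that develop under repeat dosing, cross-react with endogenous LCAT and lower HDL-C.

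On analysis, Protocol 4.8.4 says only that "ADA incidence rate and titer will be tabulated for each treatment group". SAP 3.6 goes further: "ADA incidence rate and titer will be tabulated for each treatment group at baseline and postbaseline visits". It then defines two classes for the overall post-baseline summary:

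- Persistent positive: positive at two or more post-baseline assessments at least 16 weeks apart, "or positive at last post-baseline assessment".
- Transient positive: "transient positive is defined as negative at last post-baseline assessment and positive at only one post-baseline assessment", or at two or more that span less than 16 weeks.

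Neither class refers to the Day 1 result. Neither document defines a treatment-emergent, treatment-induced or treatment-boosted category, or a titer-rise rule for the analysis.

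SAP Table 3.2-1 admits to the immunogenicity population any treated subject with "at least one serum sample for immunogenicity testing", and SAP 3.2 assesses immunogenicity data in that population. SAP 3.6 names no denominator for its percentages.

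**The concern.** Development is a change from the state before dosing. The overall summary describes only the state after dosing. A subject who carries antibody before the first dose and simply keeps it gets the same label as a subject who had none and acquired it.

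Nothing in the design prevents such subjects from entering. Exclusion criterion 16 removes people with previous rhLCAT exposure, but no criterion refers to ADA status. The confirmatory assay in Protocol 4.3.5 establishes that a positive result is specific to MEDI6012, not when the antibody arose.

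At stake is the interpretation of a secondary endpoint. In groups of six, one subject in the wrong class visibly changes the reported rate, and the overall table would not show that this had happened.

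**Working it through.** The documents state no ADA rate, precision or prevalence, so there is no planned figure to reproduce. The check reads the rules against the sampling schedule and then sizes the effect.

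**Inputs**

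- Each cohort has 8 subjects randomized 6:2 (SAP 2.2), so 6 active per cohort and 4 × 6 = 24 active in total.
- ADA samples in Cohorts 1-3: Days 1 and 15 predose, then Days 29, 43 and 71 (Protocol Table 4.2-1 footnotes).
- ADA samples in Cohort 4: Days 1 and 10 predose, then Days 24, 38 and 66 (Table 4.2-2 footnotes).
- Positive samples are confirmed, titered and tested for neutralization (Protocol 4.3.5).
- Prevalence of pre-existing ADA: not given. A range of 1% to 10% is assumed.

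**Step 1: which part of the persistent rule operates in the CSR**

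First to last scheduled post-baseline sample:

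- Cohorts 1-3: (71 − 15)/7 = 8 weeks.
- Cohort 4: (66 − 10)/7 = 8 weeks.

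The 16-week limb cannot be met on these visits. It needs the extra visits for ADA-positive subjects, and those long-term data go into an addendum. In the CSR, persistent therefore means positive at the last assessment.

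**Step 2: two subjects under the rule**

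| | Day 1 | Last assessment | SAP class |
|---|---|---|---|
| Seroconverter | negative | positive | persistent |
| Stable pre-existing antibody, titer unchanged | positive | positive | persistent |

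The by-visit tables do not separate them either, because they give group counts. With 1/6 positive at baseline and 2/6 after dosing, there could be one new case or two.

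**Step 3: size in one cohort**

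One subject is 1/6 = 16.7 percentage points. If two of six are positive after dosing and one of them was already positive without a titer rise, the post-baseline rate is 2/6 = 33.3% and the treatment-emergent rate is 1/6 = 16.7%. The shift occurs only if the baseline-positive subject also tests positive after dosing. Exact 95% intervals are wide in both cases (4.3% to 77.7% and 0.4% to 64.1%), so the issue is what the rate means more than its precision.

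**Step 4: how likely a baseline-positive subject is**

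P(at least one) = 1 − (1 − p)^n.

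| Assumed p | n = 6 (one cohort) | n = 24 (all active) |
|---|---|---|
| 1% | 5.9% | 21.4% |
| 2% | 11.4% | 38.4% |
| 5% | 26.5% | 70.8% |
| 10% | 46.9% | 92.0% |

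**Step 5: the denominator, if it is the full immunogenicity population**

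A subject with only the Day 1 sample would be counted but could not be a post-baseline positive. With one such subject among six, one positive reads 1/6 = 16.7% instead of 1/5 = 20.0%, and two positives read 2/6 = 33.3% instead of 2/5 = 40.0%. This acts in the opposite direction to Step 3. With both present, 2/6 = 33.3% becomes 1/5 = 20.0%.

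**The case against.** The strongest reply is that the information is already there. SAP 3.6 tabulates incidence and titer at baseline, data listings are sorted by subject, and the placebo subjects give a background rate. With 32 planned subjects, a careful reader could trace a Day 1 positive by hand. This stands to a point: it would be wrong to infer that ADA incidence as a whole ignores baseline. But group counts and listings do not put a subject-level rule into the one overall summary.

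Three further inferences are tempting, and the documents do not support them.

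- **That the SAP calls these positives drug-induced.** Its label is a post-baseline summary. The attribution would be the reader's, prompted by an endpoint worded as development.
- **That early drop-outs are counted as negative.** SAP 3.2 points that way, but SAP 3.6 states no denominator, and the separate programming plan, which was not available for this review, may settle it. Protocol 4.2.1 allows an ADA sample at early termination. Protocol 4.1.6 keeps dosed subjects in follow-up unless consent is withdrawn, and 4.1.7 allows replacement. A baseline-only subject is possible but needs several things to coincide.
- **That dose escalation or dose selection would be misled.** The rules in Protocol 3.1.3 and 4.3.5 use ADA results with HDL-C change, or a rising titer. None uses the persistent or transient classes, and no document sets a threshold on an ADA rate.

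It is also fair to say that the prevalence range is pure assumption and that the two distortions oppose each other, so no net direction of bias is shown.

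**Conclusion.** The baseline point holds. As written, the persistent and transient classes cannot distinguish antibody that developed in the study from antibody that was already present, although the endpoint they summarize is development. One misclassified subject is worth 16.7 points in a cohort of six active subjects. How likely that is depends on an unknown prevalence: at an assumed 1% to 10%, the chance of at least one baseline-positive subject is 6% to 47% per cohort and 21% to 92% over all 24 active subjects. These figures bound the chance of misclassification from above, because the subject must also test positive after dosing.

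The denominator point is minor and conditional. It is a gap in SAP 3.6, not a demonstrated error.

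This is a worthwhile, inexpensive correction to a descriptive secondary analysis. It does not affect the primary endpoints or the escalation rules.

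**What to change.** In SAP 3.6:

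1. Define treatment-emergent ADA as baseline-negative with a confirmed post-baseline positive, or baseline-positive with a pre-specified titer rise. Set the size of that rise from the assay's validated dilution scheme. The documents do not give the scheme, so no fold is proposed here.
2. Apply the persistent and transient classes within the treatment-emergent group only.
3. Show baseline-positive subjects without a qualifying rise in a separate row.
4. Treat nAb the same way.
5. State the denominator of the overall post-baseline rate: subjects with a baseline result and at least one post-baseline ADA result. The baseline result is needed because treatment-emergent status cannot be assigned without it.

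The cost is a few lines of SAP text and one derived flag. The Day 1 sample and the titers are already planned, so there is no extra sampling. The downside is that the rate may rest on one or two fewer subjects, so the number excluded should be shown beside it.

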3.7 Pharmacokinetics

Non-compartmental analysis will be performed for MEDI6012 treated subjects. Serum MEDI6012 mass and activity concentration-time profiles will be summarized by dose cohort. The PK parameters to be reported include C_{max} , time to reach C_{max} (T_{max}), AUC, accumulation ratio, and $t_{1/2}$. Descriptive statistics for PK parameters will be provided.

Additional PK analyses may be conducted as appropriate. If the data allow, population PK analysis will be performed but will not be reported in the clinical study report.

The PK analysis will be performed by the Clinical Pharmacology DMPK department (CPD), MedImmune LLC. Results, discussions and data interpretations of the PK analysis will be presented in a report separate from the CSR.

3.8 Exploratory Endpoints

4 INTERIM ANALYSIS

A primary analysis of the safety, immunogenicity, PK, and PD data will be conducted after the last subject has completed or dropped out prior to the last scheduled visit (Day 71 visit [Cohorts 1-3] or Day 66 [Cohort 4]) and will be reported in the CSR. The long-term followup data will be reported as an addendum to the CSR.

